3.3.6 Rationale for Efficacy Endpoints

The change in the UAS7 (see [Table 2](#) for daily assessment of Urticaria Activity Score [UAS]) has been chosen as the primary efficacy endpoint as it has been used in pivotal trials in CSU to measure reduction in CSU disease severity. The UAS7 is a summation of the average daily (a.m./p.m.) scores on the UAS (range: 0–6), which is a composite diary score with numeric severity intensity ratings on a scale of 0–3 (0 = none to 3 = intense/severe) for two domains: the intensity of the itch and the number of wheals/hives (see [Table 2](#)). The UAS will be recorded by the patient twice daily (morning and evening) in the patient Urticaria Patient Daily eDiary. UAS7 scores range from 0–42 and the minimally important difference (MID) is considered to be a reduction from baseline of ≥ 9.5 to 10.5 points (Mathias et al. 2012). The baseline UAS7 is the sum of the daily scores on the UAS over the 7 days prior to randomization (Day 1 visit for both cohorts), and the UAS7 at Day 57 is the sum of daily scores on the UAS over the 7 days prior to the Day 57 visit (for both cohorts). The same principles of calculating baseline and Day 57 weekly scores will be applied to the other weekly outcomes unless otherwise stated.

The kinetics of response to fenebrutinib will also be carefully evaluated throughout the course of the study at regular intervals (at least every 1–2 weeks for a period of 8 weeks). In addition, disease recurrence or duration of treatment benefit after study drug is withdrawn during the safety follow-up period will be measured during this study. This will provide initial guidance for the duration of therapy in future studies.

Table 2 Twice Daily Patient Assessment of CSU Disease Activity (UAS Scale)

| Score | Wheals (Hives) | Pruritus (Itch) |
|-------|-------------------------------|-----------------|
| 0 | None | None |
| 1 | Mild (1–6 hives/12 hour) | Mild |
| 2 | Moderate (7–12 hives/12 hour) | Moderate |
| 3 | Intense (> 12 hives/12 hour) | Severe |

CSU = chronic spontaneous urticaria; UAS = Urticaria Activity Score.

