4.1.1 Inclusion Criteria

Patients in Cohort 1 and 2 must meet the following criteria for study entry:

- Willing to give written informed consent, adhere to the visit schedules, comply with the study drug regimen, and meet other study requirements
- Aged 18–75 years, inclusive
- Diagnosis of CSU refractory to H1 antihistamines at the time of randomization, as defined by all of the following:
 - The presence of itch and hives for >6 consecutive weeks at any time prior to enrollment despite current use of H1 antihistamines, consistent with standard of care (i.e., up to 4 times the approved dose per local treatment guidelines) during this time period
 - UAS7 score ≥ 16 during the 7 days prior to randomization (Day 1)
 - Patients must have been on daily stable doses of H1 antihistamines, consistent with standard-of-care therapy (i.e., up to 4 times the approved dose per local treatment guidelines) for CSU starting at least 3 consecutive days immediately prior to the screening visit through Day 1 and must document current use on all visits.
 - CSU diagnosis for ≥ 6 months

- Willing and able to complete an Urticaria Patient Daily eDiary for the duration of the study
- Completion of 7 days of the Urticaria Patient Daily eDiary entries in the 7 days prior to randomization (7 of 7 days must be completed [i.e., must complete an entry every day] with up to 2 non-consecutive entries missed)
- No evidence of active or latent or inadequately treated infection with tuberculosis (TB) as defined by the following:
 - A negative QuantiFERON-TB-Gold® (QFT) performed (for German sites only: QFT is the preferred test) at the screening visit or within the 3 months prior to screening
 - If QFT is unavailable, a negative Mantoux purified protein derivative (PPD) skin test as defined by the Centers for Disease Control and Prevention guidelines, may be performed at the screening visit or within the 3 months prior to screening -AND-
 - Any additional procedures (e.g., chest X-Ray) only if required per local guidelines/standard of care to rule out latent or active TB

NOTE: A documented negative screening for TB via the PPD test or a negative QFT within 3 months prior to screening and if required per local standard of care, a chest X-ray, is sufficient and no further screening with QFT is required.

Patients with a history of Bacille Calmette-Guérin (BCG) vaccination should be screened using the QFT test, only.

- An indeterminate QFT test should be repeated.

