6. STATISTICAL CONSIDERATIONS AND ANALYSIS PLAN

The primary and secondary efficacy analyses will be based on a modified intent-to-treat (mITT) approach. All patients who received at least one dose of study drug will be included in the mITT population, with patients grouped according to the treatment assigned at randomization. Safety analyses will be conducted on the safety-evaluable population, defined as all patients who received at least one dose of study drug, with patients grouped according to the actual treatment received.

For each cohort, the final analysis of data from the 8-week, placebo-controlled period will be performed when the following two criteria have been met: 1) All patients in the cohort have either completed the Day 57 visit or discontinued from the placebo-controlled period prematurely and 2) all data from the placebo-controlled period in the cohort are in the database and have been cleaned and verified. Patients and study site personnel will remain blinded to the individual treatment assignment until after the study is completed (i.e., after all patients in both cohorts have either completed the safety follow-up period or discontinued early from the study), the database is locked, and the study analyses are final for both cohorts.

The focus of the trial is estimation and generation of hypotheses to be confirmed in future trials; therefore, Type I error control is not addressed.

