6.4 EFFICACY ANALYSES

Statistical analysis will be conducted for each cohort separately. Statistical testing will be performed as a two-sided test with a statistical significance level of 0.10. No multiplicity adjustments will be performed to control overall Type I error, and positive tests will be viewed as hypothesis generating rather than confirmatory.

Continuous longitudinal efficacy endpoints will be analyzed using a mixed model for repeated measures (MMRM) and descriptive statistics as appropriate. An unstructured covariance pattern will be specified to model the within-subject errors. Parameters will be estimated with the use of restricted maximum likelihood, and the Kenward-Roger method will be used for calculating the denominator degrees of freedom. The MMRM method assumes that data are missing at random. That is, MMRM assumes that given the statistical model and given the observed values of the endpoint, missing data are independent of the unobserved values (O'Kelly and Ratitch 2014). High correlation between successive observations on a subject allows data from subjects who dropped out to make a contribution to estimation of the effects at the final timepoint.

All MMRM models will include country, treatment group, visit, and visit by treatment group interaction as covariates.

Time-to-event endpoints will be analyzed using a Cox proportional hazards model. Categorical endpoints will be analyzed using an appropriate statistical method, such as Cochran-Mantel-Haenszel test or Fisher's exact test.

Details of all statistical methods will be provided in the Data Analysis Plans (DAP).

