6.4.1 Primary Efficacy Endpoint

The primary efficacy endpoint is the change from baseline in the UAS7 at Day 57 (Week 8).

The UAS is to be recorded twice daily (i.e., morning and evening) using an eDiary that will be provided to each patient. Scores ranging from 0 (none) to 3 (severe) will be entered for each of the two UAS domains consisting of number of wheals (hives) and intensity of pruritis (itch) resulting in a total possible score of 0 to 6 (see [Table 2](#)). The daily UAS is calculated as the average of the morning and evening scores. When either the morning or evening score is missing, the non-missing UAS for that day (morning or evening) will be used as the daily UAS, and when both the morning and evening UAS

are missing, the daily UAS will be deemed missing. The UAS7 is the sum of the daily UAS over the 7 days prior to the timepoint of interest. The baseline UAS7 will be calculated as the sum of daily UAS values over the week (7 days) prior to Day 1.

When one or more daily UAS values is missing, over the week prior to a timepoint of interest, rules for deriving UAS7 will be as follows:

- If a patient has at least 4 completed daily scores on the UAS (both domains) over the 7 days prior to the timepoint of interest, the UAS7 will be defined as the average of the available daily scores, multiplied by 7.
- If a patient has fewer than 4 completed daily scores on the UAS over the 7 days prior to the timepoint of interest, then the UAS7 will be considered missing for that timepoint.

The primary endpoint will be analyzed using a MMRM model as specified in Section 6.4. Additional model covariates will include baseline UAS7 and its interaction with visit. Missing data will be handled by the model under the missing-at-random assumption without need for imputation.

As a sensitivity analysis, an analysis-of-covariance (ANCOVA) model adjusted for country and baseline UAS7 will be fit. Missing Day 57 data will be imputed by last observation carried forward.

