6.4.2 Secondary Efficacy Endpoints

The secondary efficacy endpoints are as follows:

- Proportion of patients who are well controlled ($UAS7 \leq 6$) at Day 57
- Change from baseline in the UAS7 at Day 29 (Week 4)

These endpoints will be analyzed as specified in Section 6.4.

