Appendix 1 Schedule of Activities (Cohorts 1 and 2) (cont.)

BID=twice a day; eCRF=electronic case report form; eDiary=electronic diary (patient reported outcomes); HBcAb=hepatitis B core antibody; HBsAb=hepatitis B surface antibody; HBsAg=hepatitis B surface antigen; HCV Ab=hepatitis C antibody; *OLE* = *open-label extension*; PD=pharmacodynamic; PK=pharmacokinetic; PPD= purified protein derivative; PPI=proton pump inhibitor; QFT= QuantiFERON-TB Gold®; QTcF=QT interval corrected using Fridericia's formula; TB=tuberculosis; [REDACTED] Term.=Termination; UAS=Urticaria Activity Score; UAS7=Urticaria Activity Score over 7 days; [REDACTED]

- a Laboratory tests prior to randomization and dosing may be performed locally on Day 0, if central laboratory tests are not available due to sampling handling problems, breakage, or lab error.
- b Safety follow-up visit 4 weeks after the last dose of study drug if the patient discontinues the study and/or study treatment (per Sections 4.6.1 and 4.6.2) prior to Day 85 visit or do not enter the OLE.
- c Phone call instead of a clinic visit.
- d Morning clinic visit is required for visits on Days 1, 8, 29, 57, and 85; for other study visits, morning visits are recommended. For mandatory morning visits, the patient should be fasting (overnight, > 8 hours) prior to the first PK blood draw and/or fasting lipid panel.
- e Day 57 visit is the last day of the study treatment period; however, no study drug will be taken at the Day 57 visit. The last dose of blinded study drug will be the p.m. dose on Day 56 or the day before the Day 57 visit if it does not occur on Day 57. *If eligible, patients may enroll into the OLE study to receive their first open-label dose of fenebrutinib on Day 1 of Study GS40868 or they will proceed and return for the safety follow-up visit 4 weeks after the last dose of study drug. For patients enrolling into the OLE study, Day 1 of Study GS40868 may be the same day as the Day 57 visit in Study GS39684.*
- f Patients should be trained to use the eDiary at Day -14. At Day -7, staff should query patients for any questions they may have concerning the use of the eDiary and ensure patients understand correct usage before randomization.
- g Patient is to complete the eDiary twice daily, approximately every 12 hours (a.m./p.m.), every day for the duration of the study. The eDiary includes the UAS7 (itch score, number of hives) and other patient reported outcomes.
- [REDACTED]

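### The general MMRM in Section 6.4 omits baseline, so it is unclear which Day 29 UAS7 estimate is reported, and weekly itch and hives have no stated baseline adjustment

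*Combined protocol and SAP*

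**What the plan says.** Section 6.4 (Efficacy Analyses) assigns continuous longitudinal endpoints to an MMRM and lists its terms: "All MMRM models will include country, treatment group, visit, and visit by treatment group interaction as covariates". It then defers: "Details of all statistical methods will be provided in the Data Analysis Plans (DAP").

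Section 6.4.1 (Primary Efficacy Endpoint) says that the Day 57 UAS7 change uses the Section 6.4 model, and then extends it: "Additional model covariates will include baseline UAS7 and its interaction with visit". The statistical methods part of the synopsis does the same. The ANCOVA sensitivity analysis for the primary endpoint also adjusts for baseline UAS7.

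Section 6.4.2 (Secondary Efficacy Endpoints) lists the Day 29 UAS7 change and says only: "These endpoints will be analyzed as specified in Section 6.4".

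Section 6.4.3 (Exploratory Efficacy Endpoints) lists the weekly itch change at Days 29 and 57 and the weekly hives change at Day 57. It names no covariates and leaves further detail to the DAP. One block of that section is redacted.

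The baselines needed for adjustment are collected:
- Section 3.3.6: "The same principles of calculating baseline and Day 57 weekly scores will be applied to the other weekly outcomes unless otherwise stated".
- Section 4.1.1 requires: "Completion of 7 days of the Urticaria Patient Daily eDiary entries in the 7 days prior to randomization".
- Appendix 1: "The eDiary includes the UAS7 (itch score, number of hives) and other patient reported outcomes".

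**The concern.** Section 6.4.1 refers to Section 6.4 for the model before baseline is added, and calls the baseline terms additional. Section 6.4.2 uses the same reference and adds nothing, so its natural meaning is the model without baseline.

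Two things follow.

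- **Day 29 UAS7.** Two estimates can be produced from the same data, one adjusted and one not, and the text does not say which is reported. This is a named secondary endpoint, tested at two-sided 0.10 without multiplicity adjustment, so the choice is better fixed in advance.
- **Weekly itch and hives.** These cannot borrow the primary fit, because they are different scores with their own baselines.

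At stake is some precision, and some protection against chance baseline imbalance in small arms (30 against 15 in Cohort 1, 30 per arm in Cohort 2). This matters to the plan's stated purpose: "The focus of the trial is estimation and generation of hypotheses to be confirmed in future trials".

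**Working it through.** **1. The text, endpoint by endpoint**

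| Endpoint | Section pointed to | Baseline term stated? |
|---|---|---|
| UAS7 change, Day 57 (primary) | 6.4 plus 6.4.1 | Yes, with visit interaction |
| UAS7 change, Day 29 (secondary) | 6.4 | Not in 6.4 or 6.4.2 |
| Itch change, Days 29 and 57 (exploratory) | 6.4 general list, DAP | None visible |
| Hives change, Day 57 (exploratory) | 6.4 general list, DAP | None visible |

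The primary MMRM contains visit, visit-by-treatment and baseline-by-visit terms, so it already yields a baseline-adjusted contrast at Day 29.

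**2. The plan's own power figures**

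Inputs from Section 6.1: difference 11, SD 13, two-sided alpha 0.10, 10% loss. With 27 against 13.5 patients, Cohort 1 power is 81.4% (normal) or 80.2% (t), which agrees with the stated 80%. With 27 per arm, Cohort 2 power is 92.8% or 92.3%, slightly above the stated approximate 90%. Neither figure uses a baseline covariate, so this point changes neither.

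**3. Effect of adjustment on the Day 29 UAS7 interval**

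This is a single-visit ANCOVA approximation that ignores country and borrowing across visits. The SD of 13 and the 10% loss are stated for Day 57 and borrowed for Day 29. Baseline SD (SDb) 5 to 7 and slope of follow-up on baseline 0.25 to 0.5 are assumptions; the documents give neither.

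Unadjusted:
- Cohort 1: SE = 13 × sqrt(1/27 + 1/13.5) = 4.33; df = 40.5 − 2 = 38.5; 90% half-width 7.30.
- Cohort 2: SE = 13 × sqrt(2/27) = 3.54; df = 108 − 4 = 104; 90% half-width 5.87.

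Adjusted:
- Share of variance removed: r = (1 − slope)² × SDb² / 13².
- Adjusted SE = SE × sqrt((1 − r) × (1 + 1/(df − 2))).
- Half-width = t(0.95, df − 1) × adjusted SE.

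| SDb | Slope | r | Cohort 1 half-width | Cohort 2 half-width |
|---|---|---|---|---|
| 5 | 0.5 | 3.7% | 7.27 (−0.5%) | 5.79 (−1.4%) |
| 7 | 0.5 | 7.2% | 7.13 (−2.3%) | 5.68 (−3.2%) |
| 5 | 0.25 | 8.3% | 7.09 (−2.9%) | 5.65 (−3.8%) |
| 7 | 0.25 | 16.3% | 6.78 (−7.2%) | 5.40 (−8.1%) |
| 5 or 7 | 1 (baseline unrelated to change) | 0 | 7.41 (+1.4%) | 5.90 (+0.5%) |

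At slope 0.75, Cohort 1 is 0.5 to 1.0% wider (7.34 to 7.37) and Cohort 2 is about unchanged (5.85 to 5.87). Assuming no loss at Day 29 (30 against 15; 30 per arm), the narrowing over the main range is 0.6 to 7.4% and 1.4 to 8.1%.

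**4. The same loss seen as chance imbalance (not an additional loss)**

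In Cohort 1, the SE of the baseline difference is SDb × sqrt(1/27 + 1/13.5) = 1.67 to 2.33 points. An imbalance of that size moves the unadjusted Day 29 difference by (1 − slope) times as much, that is by 0.8 to 1.75 points.

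**5. Itch and hives**

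The documents give no SD for either score, so no figure can be computed.

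**The case against.** The case on the other side is substantial.

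- **Day 29 is largely handled.** Days 29 and 57 are two visits of one longitudinal response, and the primary model adjusts both. No text says that a second fit with baseline removed will be run. A reader might infer that the Day 29 endpoint will definitely be analysed without adjustment. The documents do not go that far: they leave open which estimate is reported. This stands, and it reduces the Day 29 part to a clarification.
- **Detail is deferred and partly redacted.** The Section 6.4 list can be read as a minimum, to which endpoint-specific terms are added, as Section 6.4.1 does. The DAP is not available here, and part of Section 6.4.3 is blacked out. For itch and hives the point therefore rests on the general list plus silence, and it cannot be said that the plan lacks the adjustment. This stands.
- **Section 6.4 might be meant to include 6.4.1.** This is possible, but Section 6.4.1 itself uses the reference for the model without baseline. If the wider reading is intended, one sentence settles it.
- **The gain is small, assumed and not always positive.** This stands. Three of the four main Cohort 1 scenarios gain less than 3%, and if baseline is unrelated to change the interval widens.
- **The quantified endpoint is the one already covered by the primary fit.** This also stands: every figure is for Day 29 UAS7, and the gap for itch and hives is unquantified.

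A reader might also infer that the unadjusted estimates are biased. With complete data, randomisation keeps them unbiased. With dropout, this depends on data being missing at random given the fitted model, and leaving baseline out changes that condition. The documents do not show a bias.

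**Conclusion.** The point holds as a low-priority improvement. Followed literally, the text calls for an unadjusted Day 29 UAS7 estimate beside an adjusted one that already exists, and it shows no baseline-adjusted model for three exploratory endpoints whose baselines are collected.

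For Day 29 UAS7, adjustment narrows the 90% interval by about 0.5 to 7% in Cohort 1 and 1.4 to 8% in Cohort 2. If baseline carries no information on change, the cost is a widening of about 1.4% and 0.5%. These ranges depend on the assumed baseline SD and slope, and on carrying the Day 57 SD and loss over to Day 29.

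The primary analysis, the stated power and the decision rules are unaffected. Confidence is high on how the text reads for Day 29, lower for itch and hives, and medium on the size of the gain.

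**What to change.** 1. In Section 6.4, add the endpoint's own baseline value and its interaction with visit to the covariates of every change-from-baseline MMRM.
2. In Section 6.4.2, state that the Day 29 UAS7 contrast is taken from the primary MMRM.

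Either sentence may go into the DAP instead. If the DAP already contains them, confirming this is enough.

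The cost is two sentences and a few degrees of freedom. No new data are needed. No patient should drop out of a model for want of a baseline, because an entry is required on each of the 7 days before randomisation, and Section 6.4.1 lets one entry stand for the day when the other is missed.

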6.4.1 Primary Efficacy Endpoint

The primary efficacy endpoint is the change from baseline in the UAS7 at Day 57 (Week 8).

The UAS is to be recorded twice daily (i.e., morning and evening) using an eDiary that will be provided to each patient. Scores ranging from 0 (none) to 3 (severe) will be entered for each of the two UAS domains consisting of number of wheals (hives) and intensity of pruritis (itch) resulting in a total possible score of 0 to 6 (see [Table 2](#)). The daily UAS is calculated as the average of the morning and evening scores. When either the morning or evening score is missing, the non-missing UAS for that day (morning or evening) will be used as the daily UAS, and when both the morning and evening UAS

are missing, the daily UAS will be deemed missing. The UAS7 is the sum of the daily UAS over the 7 days prior to the timepoint of interest. The baseline UAS7 will be calculated as the sum of daily UAS values over the week (7 days) prior to Day 1.

When one or more daily UAS values is missing, over the week prior to a timepoint of interest, rules for deriving UAS7 will be as follows:

- If a patient has at least 4 completed daily scores on the UAS (both domains) over the 7 days prior to the timepoint of interest, the UAS7 will be defined as the average of the available daily scores, multiplied by 7.
- If a patient has fewer than 4 completed daily scores on the UAS over the 7 days prior to the timepoint of interest, then the UAS7 will be considered missing for that timepoint.

The primary endpoint will be analyzed using a MMRM model as specified in Section 6.4. Additional model covariates will include baseline UAS7 and its interaction with visit. Missing data will be handled by the model under the missing-at-random assumption without need for imputation.

As a sensitivity analysis, an analysis-of-covariance (ANCOVA) model adjusted for country and baseline UAS7 will be fit. Missing Day 57 data will be imputed by last observation carried forward.

6.4.2 Secondary Efficacy Endpoints

The secondary efficacy endpoints are as follows:

- Proportion of patients who are well controlled ($UAS7 \leq 6$) at Day 57
- Change from baseline in the UAS7 at Day 29 (Week 4)

These endpoints will be analyzed as specified in Section 6.4.

6.4.3 Exploratory Efficacy Endpoints

The exploratory efficacy endpoints include the following:

- Change from baseline in the weekly itch score at Day 29
- Change from baseline in the weekly itch score at Day 57
- Change from baseline in the weekly hives score at Day 57
- Proportion of patients who are well controlled ($UAS7 \leq 6$) at Day 29
- Proportion of patients who achieve complete response ($UAS7 = 0$) at Day 29
- Proportion of patients who achieve complete response ($UAS7 = 0$) at Day 57
- Proportion of patients achieving MID in UAS7 at Day 57 (reduction from baseline ≥ 11 points)
- Proportion of patients achieving MID in the weekly itch score at Day 57 (reduction from baseline ≥ 5 points)

- Time to achieving MID in UAS7 (reduction from baseline ≥ 11 points)

[REDACTED]

Further details on the analysis of exploratory endpoints will be included in the DAP.

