6.1 DETERMINATION OF SAMPLE SIZE

6.1.1 Cohort 1: Pilot Assessment

The purpose of this cohort is to evaluate the efficacy of fenebrutinib at 200 mg PO BID compared with placebo in improving the UAS7. Point and interval estimates of the

change from baseline of the UAS7 within each treatment group as well as of the difference in change from baseline of the UAS7 between treatment groups will be presented.

The cohort will enroll approximately 45 patients. Patients will be randomized in a 2:1 ratio to receive treatment with either fenebrutinib or placebo. The sample size of approximately 30 patients in the fenebrutinib arm and 15 patients in the placebo arm provides approximately 80% power to detect an 11-point difference in the UAS7 change from baseline at Day 57 between treatment groups under the following assumptions:

- The absolute change from baseline at Day 57 is normally distributed with a standard deviation of 13.
- Two-sided alpha is 0.10.
- Dropout rate at Day 57 is 10%, leading to a 10% loss of information.

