6.1.2 Cohort 2: Dose-Ranging Assessment

The purpose of this cohort is estimation and hypothesis generation regarding the dose-ranging effects of fenebrutinib compared with placebo in improving the UAS7. Point and interval estimates of the change from baseline of the UAS7 within each treatment group as well as of the difference in change from baseline of the UAS7 between treatment groups vs placebo will be presented.

The cohort will enroll approximately 120 patients. Patients will be randomly allocated in a 1:1:1:1 ratio to receive treatment with one of three dose levels of fenebrutinib or placebo. The sample size of approximately 30 in each arm provides approximately 90% power to detect an 11-point difference in the UAS7 change from baseline at Day 57 between treatment groups, under the following assumptions:

- The absolute change from baseline at Day 57 is normally distributed with a standard deviation of 13
- Two-sided alpha is 0.10
- Dropout rate at Day 57 is 10%, leading to a 10% loss of information.

The overall sample size may be adjusted depending on the outcome of a planned interim analysis for Cohort 1 (see Section 6.8), which will include an evaluation of these assumptions.

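### Do the two exploratory UAS7 endpoints need changing because they call a reduction of at least 11 points the MID, when the protocol gives the MID as 9.5 to 10.5?

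*Combined protocol and SAP*

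**What the plan says.** Section 3.3.6, which gives the rationale for the efficacy endpoints, cites a published study and says that "the minimally important difference (MID) is considered to be a reduction from baseline of ≥ 9.5 to 10.5 points".

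Section 6.4.3 defines two exploratory endpoints under the name MID in UAS7: "Proportion of patients achieving MID in UAS7 at Day 57 (reduction from baseline ≥ 11 points" and "Time to achieving MID in UAS7 (reduction from baseline ≥ 11 points". The synopsis and Table 1 in Section 2 give the same two endpoints with the same cut-off. Section 6.4.3 adds that "Further details on the analysis of exploratory endpoints will be included in the DAP"; the DAP (data analysis plan) is not among the documents. Text is also redacted just after the endpoint list and elsewhere in Section 3.3.

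The figure of 11 UAS7 points appears in one other role, as the difference between groups used for sample size: "approximately 80% power to detect an 11-point difference in the UAS7 change from baseline at Day 57 between treatment groups" in Section 6.1.1, and "approximately 90% power to detect an 11-point difference in the UAS7 change from baseline at Day 57 between treatment groups" in Section 6.1.2. Neither section links that difference to the MID.

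**The concern.** The same term, for the same score and the same quantity (a patient's own reduction from baseline), carries two values. The larger value, 11, lies outside the whole range given for the smaller. The figure of 11 appears in three places, so it is not a stray typing error.

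The scale does not force the choice. Section 6.4.1 states that "The daily UAS is calculated as the average of the morning and evening scores". With whole-number morning and evening scores, a complete week therefore moves in half-point steps, and reductions of 9.5, 10 and 10.5 can all occur. A patient who improves by exactly 10.5 reaches the upper end of the stated MID and still counts as a non-achiever in both endpoints.

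At stake is what a reported proportion achieving MID means. Section 6 says the trial is meant to estimate effects and to generate hypotheses for later trials. A reader could carry forward a responder rate that is lower than the protocol's own MID would give.

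**Working it through.** **1. The plan's own use of 11 points.** The responder cut-off has no stated figure to reproduce. The power statements do, and they show that the 11 there is a separate quantity. Inputs from Sections 6.1.1 and 6.1.2: difference 11, SD 13, two-sided alpha 0.10, 10% loss of information. Power is Φ(Δ / (SD × √(1/n₁ + 1/n₂)) − 1.645).

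- Cohort 1, n = 27 and 13.5: standard error 13 × √(1/27 + 1/13.5) = 4.33; 11/4.33 = 2.54; power 81.4% (80.2% with the t distribution). The plan says about 80%.
- Cohort 2, n = 27 and 27: standard error 3.54; 11/3.54 = 3.11; power 92.8% (92.3% with t). The plan says about 90%, so it errs slightly on the safe side.

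These figures concern the difference in mean change. They do not depend on any responder cut-off.

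**2. Is the rule ambiguous?** Synopsis, Table 1 and Section 6.4.3 each print at least 11 beside both endpoints. Section 3.3.6 gives a range and sets no responder rule. Any responder endpoint has to pick one number, and the three places that do so agree.

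**3. How many patients lie between the two values?** Take the reduction as normal with SD 13. The documents give no mean reductions, so 0 to 20 points is an assumption. The share of an arm in [c, 11) is Φ((11 − m)/13) − Φ((c − m)/13).

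| Mean reduction m | in [10.5, 11) | in [9.5, 11) |
|---|---|---|
| 0 | 1.09% | 3.37% |
| 5 | 1.39% | 4.24% |
| 9 | 1.52% | 4.58% |
| 11 | 1.53% | 4.59% |
| 16 | 1.41% | 4.17% |
| 20 | 1.19% | 3.47% |

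In an arm of 30 the extremes are 30 × 0.0109 = 0.3 to 30 × 0.0153 = 0.5 patients, and 30 × 0.0337 = 1.0 to 30 × 0.0459 = 1.4 patients. After 10% dropout (27 evaluable) the counts are slightly lower.

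**4. Does the treatment comparison move?** Active minus placebo, in percentage points, for an 11-point gap in means:

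| Assumed means (placebo/active) | cut-off 11 | 10.5 | 9.5 |
|---|---|---|---|
| 0/11 | 30.13 | 30.57 | 31.35 |
| 5/16 | 32.75 | 32.78 | 32.68 |
| 9/20 | 31.68 | 31.35 | 30.57 |

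The shift runs from 31.35 − 31.68 = −0.3 to 30.57 − 30.13 = +0.4 at 10.5, and from 30.57 − 31.68 = −1.1 to 31.35 − 30.13 = +1.2 at 9.5. The sign depends on the assumed means.

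**5. Compared with sampling error.** The standard error of a difference in proportions is √(p₁(1 − p₁)/n₁ + p₂(1 − p₂)/n₂). With p = 0.20 and 0.50 and 30 per arm it is √(0.16/30 + 0.25/30) = 0.117, about 12 points. In Cohort 1 with p = 0.44 (n = 15) and 0.76 (n = 30) it is √(0.246/15 + 0.182/30) = 0.150, or 15 points. The largest shift is about a tenth of the smaller of these.

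**6. Does the normal model mislead on a bounded scale?** Reductions were rounded to 0.5 and clipped to the 0 to 42 scale under three assumed baselines: fixed at 30; normal with mean 31 and SD 7, clipped to 16–42; uniform on 16–42. The shares were again 1.1% to 1.5% and 3.4% to 4.6%, with shifts within 0.4 and 1.2 points. Entry requires "UAS7 score ≥ 16 during the 7 days prior to randomization (Day 1", so a reduction of 11 is open to every patient and the floor does not bind there.

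**The case for a change.** The strongest case for acting is that the contradiction is plain on the page and cheap to remove. Rounding 10.5 up to 11 may explain it, but the protocol does not say so and the half-point scale does not require it. Redacted text or the DAP may hold a reason, but Section 3.3.6 is readable and gives another number. In a trial aimed at estimation, a labelled proportion should mean what the protocol says the label means. Renaming the endpoints, and reporting cut-offs of 10.5 and 9.5 as supplements, would settle it.

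The textual point stands in full. The case for action is weaker.

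- The rename alters no computed result, because the cut-off of 11 would be kept.
- Section 9.6 requires ethics approval, and regulatory approval where locally required, for any amendment beyond immediate hazards and logistical or administrative matters. A stand-alone amendment for a label is poor value.
- The supplements would add 2 cut-offs × 2 endpoints × 4 active-placebo comparisons (one in Cohort 1, three in Cohort 2) = 16 further comparisons without multiplicity adjustment (Section 6.4). The figures above predict that they would show almost nothing.
- A stricter cut-off cannot bring a patient's event time forward, so time to MID can only lengthen or stay the same. The size of that effect was not calculated. Section 3.3.6 describes evaluation every one to two weeks. If event times are read on such a grid, a patient who passes 10.5 and 11 in the same interval has the same event time under both.

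**Conclusion.** The mismatch is real, but the plan needs no change. The rule is stated without ambiguity in three places, and it is conservative, because everyone counted at 11 has met the stated MID. Under the protocol's SD of 13 and assumed mean reductions of 0 to 20, the share of an arm meeting the stated MID is understated by about 1 to 5 percentage points, at most 1.4 patients in 30. The difference between arms moves by at most about 1.2 points in either direction for an assumed 11-point gap in means.

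The mean reductions and the baselines in the bounded check are assumptions. Extending the means to 26 gives shares of 0.8% to 1.5% and 2.2% to 4.6%, with shifts of at most 0.7 and 2.1 points. That extension puts 10.9% of a normal arm beyond the largest reduction the scale allows, so it is not the main range.

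Both endpoints are exploratory, and Section 6.4 treats positive tests as hypothesis generating. The primary endpoint, the secondary endpoints and the power do not use this cut-off. A table that prints it beside the result, as the endpoint definitions already do, tells the reader what was counted.
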